7.1.6. Rescue Therapy

The initiation of non-study drug therapy to treat worsening of psoriasis, or flare of previously inactive skin disease, is strongly discouraged throughout the treatment period. However, should rescue therapy be required for the safety and well-being of the subject, such use will be permitted. The subject may remain on study drug, unless the rescue therapy is any therapy that may jeopardize the subject's safety if study drug is continued, in the investigator's and/or Sponsor's opinion. Because the study is not a randomized trial, any subjects that are required to be placed on rescue therapy, but continue in the study will have any data after rescue treated as missing values. Missing values will be imputed from the average of all subjects completed for those data points. Alternatively if rescue therapy is required for > 50% of the patients, then these individuals would be analyzed as a separate cohort of patients and will not be analyzed in the grouped data.

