9. STATISTICAL ANALYSES

9.1. Overview

The objective of the statistical analysis will be to evaluate change in aberrant inflammatory profiles of activated blood monocytes (aberrant-monocyte endotype patients (AM-endotype). Subjects with moderate to severe plaque psoriasis will be treated with oral apremilast (Otezla) with standard dosing for 16 weeks. For each subject, we will identify a target biomarker of abnormally elevated monocytes, among intermediate, doublets, and platelet doubles. Each subject will thus have one identified monocyte biomarker for which relative percent change will be its basis for analysis in the primary outcome. If more than one category is abnormally elevated, then among abnormally elevated monocyte biomarkers we will first select doublets if elevated. If not, then we will select intermediate monocytes. For each of the selected abnormally elevated monocyte biomarkers, our focus will be on relative percent reduction. We will specifically assess change from baseline to 16 weeks by computing relative percent reduction for each subject being treated. Note for example that a change of 1.5% to 1.2% is $(1 - (1.2/1.5)) * 100\% = 20\%$ reduction. The median and other summary statistics of these percent change values will be computed. Wilcoxon's signed rank test will be used to evaluate the null hypothesis of the median percent change being 0. In other words, we will test whether or not there has been a reduction in abnormally elevated monocytes.

Secondarily, in an exploratory manner, we will longitudinally model these percent change values across time points (baseline, 4, 8, 12, and 16 weeks), to assess trajectory of percent change values. We will test for time effects, and consider post-hoc pairwise analyses of time points. Time will be considered as both a continuous covariate with slope parameter, as well as a categorical variable, which does not require linearity assumptions.

In analyses treating time as a continuous variable, actual measurements of time (as compared to fixed time points by week) will be used in the analyses.

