Other outcomes such as PASI will be analyzed similarly. Note that we will also correlate change in our abnormally elevated monocyte markers at various time points with change in PASI, to explore possible mechanistic associations. For a two-sided Wilcoxon test with Type I error of 0.05, power is 0.80 if the effect size is 0.60 or greater (assuming an underlying normal distribution). For 20% median reduction, as long as standard deviation of percent change is not larger than 33%, we will have effect size of at least 0.60. These are plausible assumptions given our prior work on treatment related monocyte reductions [40].

Because the study is not a randomized trial, any subjects that are required to be placed on rescue therapy, but continue in the study will have any data after rescue treated as missing values and these missing values will be imputed from the average of all subjects completed. Alternatively if rescue therapy is required for > 50% of the patients, then these individuals would be analyzed as a separate cohort of patients and will not be analyzed in the grouped data.

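### Filling post-rescue values with the completers' average breaks the 5% level of the primary signed-rank test once patients are rescued

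*Combined protocol and SAP*

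**What the plan says.** Section 9.1 selects one target biomarker per patient ("Each subject will thus have one identified monocyte biomarker") and computes its percent reduction from baseline to Week 16. The "signed rank test will be used to evaluate the null hypothesis of the median percent change being 0". The same section states a two-sided Type I error of 0.05 and power of 0.80 at an effect size of 0.60, "assuming an underlying normal distribution".

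For rescued patients who continue, Section 9.1 treats later data as missing and adds: "these missing values will be imputed from the average of all subjects completed". Section 7.1.6 words it slightly differently: "Missing values will be imputed from the average of all subjects completed for those data points". Section 7.1.6 also says that starting other treatment for worsening psoriasis "is strongly discouraged throughout the treatment period", but allows it when needed. There is an upper limit to the rule: "if rescue therapy is required for > 50% of the patients, then these individuals would be analyzed as a separate cohort of patients", and they leave the grouped analysis.

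Neither section says whether percent change or the measured biomarker value is averaged. If it is the measured value, neither says whether only completers with the same target biomarker count. No variance adjustment, multiple imputation or analysis without the filled values is described.

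**The concern.** If percent changes are averaged, every filled value is a copy of one number and takes the sign of the completers' mean. If measured values are averaged, the filled percent changes differ only through each patient's own baseline. Either way the test counts each filled value as a separate patient although nothing was observed. The error rate should therefore exceed 0.05 and grow with the number filled, even when rescue has nothing to do with the biomarker.

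The undefined scale matters as well. One reading inflates false reductions and apparent power. The other can produce mainly false increases and reduce power. That choice should not be open when the data are analysed.

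A lesser point is that the 50% rule lets a post-treatment event decide the primary analysis set. With 12 of 25 rescued (48%), all 25 are analysed, 12 of them with filled values. With 13 rescued (52%), only the other 12 are.

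**Working it through.** **Inputs.** From the documents: 25 treated patients (Section 6.1; the power sentence gives no n), two-sided 0.05, SD of percent change 33%, normal distribution (Section 9.1). Assumed: the number rescued, the baseline coefficient of variation (CV), and rescue unrelated to the biomarker unless stated.

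**The plan's own figure.** The effect size is 20/33 = 0.606, stated as 0.60. Simulating the signed-rank test at n = 25 and effect 0.60 gives power 0.803. A noncentral t with n scaled by 3/π gives 0.801. The stated 0.80 reproduces. Type I error with nothing filled is 0.0485.

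**Error with filled values, no true effect.** With *k* patients filled:

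- Percent-change fill: each filled value is the mean percent change of the other 25 − *k*.
- Raw-value fill: each filled reduction is 1 − *m*/*b*, where *m* is the completers' mean Week 16 value and *b* the patient's own baseline. One biomarker and a lognormal baseline are assumed.

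Two-sided error (tie-corrected variance, cut-off 1.96; 40,000 to 60,000 trials per cell):

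| Filled | Percent-change fill | Raw, CV 0.2 | Raw, CV 0.4 | Raw, CV 0.6 |
|---|---|---|---|---|
| 1 | 0.061 | 0.059 | 0.056 | 0.053 |
| 3 | 0.093 | 0.081 | 0.072 | 0.069 |
| 5 | 0.143 | 0.115 | 0.097 | 0.095 |
| 8 | 0.255 | 0.178 | 0.147 | 0.148 |
| 12 | 0.515 | not run | not run | not run |

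Leaving rescued patients out gives 0.048 to 0.051. With 5 filled on the percent-change scale, other assumed shapes give 0.125 (uniform), 0.165 (t, 3 df) and 0.171 (Laplace).

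**Direction, 5 filled (nominal 0.025 per side).** Percent-change fill: 0.072 false reductions and 0.071 false increases. Raw fill at CV 0.2, 0.4 and 0.6: reductions 0.049, 0.031 and 0.022; increases 0.066, 0.066 and 0.072. The raw fill leans towards increases because, for a lognormal baseline, the mean of *m*/*b* is 1 + CV² under no effect: 1.04, 1.16 and 1.36.

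**Power at effect 0.60 (0.80 with none rescued).**

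| Rescued | Percent-change fill | Raw, CV 0.2 | Raw, CV 0.4 | Raw, CV 0.6 | Left out |
|---|---|---|---|---|---|
| 3 | 0.84 | 0.80 | 0.72 | 0.64 | 0.75 |
| 5 | 0.86 | 0.80 | 0.67 | 0.55 | 0.70 |
| 8 | 0.88 | 0.78 | 0.60 | 0.44 | 0.63 |

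**If rescue goes to poorer biomarker responders** (assumed correlation 0.3 to 0.5, 5 rescued), false reductions are 0.15 to 0.24 with the percent-change fill, 0.05 to 0.18 with the raw fill and 0.06 to 0.11 with patients left out. Part of this is therefore informative missingness and not the fill. At correlation −0.3 the percent-change fill reverses: 0.031 reductions, 0.154 increases.

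**The proposed repair.** Twenty proper imputations of the Week 16 log ratio were converted back to percent change. The signed-rank z was pooled as mean(z)/√(1 + (1 + 1/20)B), with B the between-imputation variance and Rubin degrees of freedom (8,000 trials per cell). With 1 to 8 rescued, including rescue tied to the patient's earlier biomarker value:

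- Normal percent change: error 0.037 to 0.050 (complete data 0.043 to 0.053).
- Lognormal ratio with the same SD: 0.052 to 0.063 (complete data 0.055 to 0.068).
- Imputing from baseline only: 0.040 to 0.050 and 0.053 to 0.062 respectively.

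**The case against.** - **The rescue rate is assumed.** This stands. The documents give none, rescue is discouraged, and Section 11 lists lack of efficacy as a reason to discontinue, so some worsening patients may never meet the rule. The size is therefore conditional. The mechanism is not, and the 50% limit allows up to 12 of 25 values to be filled.
- **Under the raw-value reading, false claims of benefit barely rise.** True at CV 0.4 to 0.6, where false reductions with 5 filled are 0.022 to 0.031 against 0.025. The stated test is two-sided, though, and its level is still broken. In that setting the same fill also cuts power to 0.67 or 0.55.
- **Leaving rescued patients out is simpler.** If rescue is uninformative and percent change is normal, that holds the level with slightly more power than the repair. It does not hold once rescue depends on earlier biomarker values, where its error reaches 0.19. Multiple imputation is preferable, but removing the fill matters most.
- **Dropping the 50% rule costs power.** This stands. In one check at 13 rescued (normal percent change, pre-rescue correlation 0.5, 1,500 trials), the repair had error 0.047 and power of about 0.30. Analysing the 12 unrescued patients has exact-test power 0.43. This change is separable from removing the fill.
- **Platelet aggregates are not named in the by-visit monocyte lists** (Section 4, Section 5). Pre-rescue values may therefore be lacking for patients with that target. Baseline-only imputation covers them.
- **It is a pilot.** The plan nevertheless states a 0.05 test and 80% power for its primary outcome.

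**Conclusion.** The concern holds. The rule is wrong as written and should be fixed before analysis. With at least one rescued patient who continues, the primary p-value cannot be read at two-sided 0.05. With 5 of 25 filled, the error is about 0.09 to 0.14 across the two readings, assuming SD 33%, normal percent change, no true effect and uninformative rescue. Heavier tails raise the upper end to about 0.17. The excess is small with one rescued patient and absent with none.

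Bias towards a reduction arises only if rescue tracks poorer biomarker response, which the documents do not show. The same condition applies to the 50% rule: with uninformative rescue, the error among 12 analysed patients is about 0.05. At correlations of 0.3 to 0.5, false reductions are 0.13 to 0.29.

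**What to change.** Only the data-handling sentences in Sections 7.1.6 and 9.1 need to change.

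1. Delete the completer-average fill and keep post-rescue values missing.
2. Multiply impute the Week 16 value of the patient's own target biomarker from that patient's baseline and pre-rescue visits, using the log ratio to baseline as the imputation scale only.
3. Convert each imputed value back to percent change, run the planned signed-rank test in each imputed set, and pool the standardised statistic by Rubin's rules.
4. State the missing-at-random assumption, and that a patient rescued before Week 4 has only a baseline to impute from.
5. Add a sensitivity analysis using the observed post-rescue values of patients who continue. If rescue depends on the unseen Week 16 value itself (correlation 0.5), the repair gives 0.02 to 0.08 false reductions with 3 to 8 rescued, against 0.08 to 0.40 for the percent-change fill.
6. Keep the longitudinal model ("Secondarily, in an exploratory manner, we will longitudinally model these percent change values across time points") as supportive; it does not replace the primary test.
7. Preferably keep all treated patients in the primary analysis at any rescue rate, and describe rescued and never-rescued subsets separately. This step carries the power cost noted at 13 rescued.

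**Cost.** No extra visits are needed, since Section 5 already collects monocyte labs at each visit; confirm that these include platelet aggregates. At effect 0.60 with 3, 5 and 8 rescued, power is 0.72–0.74, 0.66–0.69 and 0.53–0.59 if percent change is normal (0.80 with complete data). If the ratio is lognormal, it is 0.79–0.81, 0.75–0.78 and 0.67–0.71 (0.84 with complete data). Under normality, imputing percent change directly has somewhat more power (0.75–0.77, 0.71–0.74, 0.65–0.68). Its error reached 0.10, against 0.085 with complete data, for a strongly skewed ratio (log SD 0.6) with 8 rescued and rescue tied to the earlier visit. The log scale is preferred for that reason.

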9.2. Background and Demographic Characteristics

Subjects' age, weight, height and other continuous demographics and baseline characteristics will be summarized using descriptive statistics (n, mean, median, standard deviation, minimum, and maximum), while gender, race, and other categorical variables will be summarized with frequency tabulations. Medical history data will be summarized using frequency tabulations.

9.3. Subject Disposition

Subject disposition (analysis population allocation, entered, completed, discontinued, along with primary reason for discontinuation) will be summarized using frequency and percent by phase. A summary of subjects randomized by site will be provided. Protocol violations/deviations will be summarized using frequency tabulations.

10. ADVERSE EVENTS

10.1. Monitoring, Recording and Reporting of Adverse Events

An adverse event (AE) is any noxious, unintended, or untoward medical occurrence that may appear or worsen in a subject during the course of a study. It may be a new intercurrent illness, a worsening concomitant illness, an injury, or any concomitant impairment of the subject's health, including laboratory test values (as specified by the criteria below), regardless of etiology. Any worsening (i.e., any clinically significant adverse change in the frequency or intensity of a pre-existing condition) should be considered an AE. A diagnosis or syndrome should be recorded on the AE page of the eCRF rather than the individual signs or symptoms of the diagnosis or syndrome.

An overdose, accidental or intentional, whether or not it is associated with an AE, or abuse, withdrawal, sensitivity or toxicity to an investigational product should be reported as an AE. If an overdose is associated with an AE, the overdose and adverse event should be reported as separate terms.

If the sequela of an overdose is an SAE, then the sequela must be reported on an SAE report form. The overdose resulting in the SAE should be identified as the cause of the event on the SAE report form but should not be reported as an SAE itself.

All subjects will be monitored for AEs during the study. Assessments may include monitoring of any or all of the following parameters: the subject's clinical symptoms, laboratory, pathological, radiological or surgical findings, physical examination findings, or other appropriate tests and procedures.

All AEs will be recorded by the Investigator from the time the subject signs informed consent to 28 days after the last dose of Otezla. AEs and serious adverse events (SAEs) will be recorded on the AE page of the eCRF and in the subject's source documents. All SAEs must be reported to Amgen Drug Safety within 24 hours of the Investigator's knowledge of the event by facsimile, or other appropriate method, using the SAE Report Form, or approved equivalent form.

Psoriasis flare and psoriasis rebound, will be captured as adverse events. General worsening of psoriasis should be considered a lack of therapeutic effect and will not be captured as an adverse event.

10.2. Evaluation of Adverse Events

A qualified Investigator will evaluate all adverse events as to:

10.2.1. Seriousness

A serious adverse event (SAE) is any AE occurring at any dose that:

- Results in death;
- Is life-threatening (i.e. in the opinion of the Investigator, the subject is at immediate risk of death from the AE);
- Requires inpatient hospitalization or prolongation of existing hospitalization (hospitalization is defined as an inpatient admission, regardless of length of stay);
- Results in persistent or significant disability/incapacity (a substantial disruption of the subject's ability to conduct normal life functions);
- Is a congenital anomaly/birth defect;
- Constitutes an important medical event.

Important medical events are defined as those occurrences that may not be immediately life threatening or result in death, hospitalization, or disability, but may jeopardize the subject or require medical or surgical intervention to prevent one of the other outcomes listed above. Medical and scientific judgment should be exercised in deciding whether such an AE should be considered serious.

Events **not considered** to be SAEs are hospitalizations for:

- A standard procedure for protocol therapy administration. However, hospitalization or prolonged hospitalization for a complication of therapy administration will be reported as an SAE.
- Routine treatment or monitoring of the studied indication not associated with any deterioration in condition.
- The administration of blood or platelet transfusion as routine treatment of studied indication. However, hospitalization or prolonged hospitalization for a complication of such transfusion remains a reportable SAE.
- A procedure for protocol/disease-related investigations (e.g., surgery, scans, endoscopy, sampling for laboratory tests, bone marrow sampling). However, hospitalization or prolonged hospitalization for a complication of such procedures remains a reportable SAE.
- Hospitalization or prolongation of hospitalization for technical, practical, or social reasons, in absence of an AE.
- A procedure that is planned (i.e., planned prior to starting of treatment on study); must be documented in the source document and the eCRF. Hospitalization or prolonged hospitalization for a complication remains a reportable SAE.
- An elective treatment of a pre-existing condition unrelated to the studied indication.
- Emergency outpatient treatment or observation that does not result in admission, unless fulfilling other seriousness criteria above.

If an AE is considered serious, both the AE page/screen of the eCRF and the SAE Report Form must be completed.

For each SAE, the Investigator will provide information on severity, start and stop dates,

relationship to IP, action taken regarding IP, and outcome.

10.2.2. Severity / Intensity

For both AEs and SAEs, the Investigator must assess the severity / intensity of the event.

Mild

- Asymptomatic or mild symptoms; clinical or diagnostic observations only
- Intervention not indicated
- Activities of daily living (ADLs) minimally or not affected
- No or minimal intervention/therapy may be required

Moderate

- Symptom(s) cause moderate discomfort
- Local or noninvasive intervention indicated
- More than minimal interference with ADLs, but able to carry out daily social and functional activities
- Drug therapy may be required

Severe (could be non-serious or serious)

- Symptoms causing severe discomfort/pain
- Symptoms requiring medical/surgical attention/intervention
- Interference with ADLs, including inability to perform daily social and functional activities (e.g., absenteeism and/or bed rest)
- Drug therapy is required

The term “severe” is often used to describe the intensity of a specific event (as in mild, moderate or severe myocardial infarction); the event itself, however, may be of relatively minor medical significance (such as severe headache). This criterion is *not* the same as “serious” which is based on subject/event *outcome* or *action* criteria associated with events that pose a threat to a subject’s life or functioning.

Seriousness, not severity, serves as a guide for defining regulatory obligations.

10.2.3. Causality

The Investigator must determine the relationship between the administration of IP and the occurrence of an AE/SAE as Not Suspected or Suspected as defined below:

Not suspected: The temporal relationship of the adverse event to IP administration makes **a causal relationship unlikely or remote**, or other medications, therapeutic interventions, or underlying conditions provide a sufficient explanation for the observed event.

Suspected: The temporal relationship of the adverse event to IP administration makes **a causal relationship possible**, and other

medications, therapeutic interventions, or underlying conditions do not provide a sufficient explanation for the observed event.

If an event is assessed as suspected of being related to a comparator, ancillary or additional IP that has not been manufactured or provided by Amgen, please provide the name of the manufacturer when reporting the event.

10.2.4. Duration

For both AEs and SAEs, the Investigator will provide a record of the start and stop dates of the event.

10.2.5. Action Taken

The Investigator will report the action taken with Otezla as a result of an AE or SAE, as applicable (e.g., discontinuation of IP, as appropriate) and report if concomitant and/or additional treatments were given for the event.

10.2.6. Outcome

All SAEs that have not resolved upon discontinuation of the subject's participation in the study must be followed until recovered, recovered with sequelae, not recovered (death due to another cause), or death (due to the SAE).

10.3. Abnormal Laboratory Values

An abnormal laboratory value is considered to be an AE if the abnormality:

- results in discontinuation from the study;
- requires treatment, modification/ interruption of Otezla dose; or
- is judged to be of significant clinical importance.

Regardless of severity grade, only laboratory abnormalities that fulfill a seriousness criterion need to be documented as a serious adverse event.

If a laboratory abnormality is one component of a diagnosis or syndrome, then only the diagnosis or syndrome should be recorded on the AE page/screen of the eCRF. If the abnormality was not a part of a diagnosis or syndrome, then the laboratory abnormality should be recorded as the AE.

